**Table 7.4.4.2. Overall Summary of 'Not-Related' AEs (Subject Level)**

N=300	
[P4] Subjects with at least 1 'not-related' AE	n (%)
[P4_i_4]: Intensity of adverse event, among Subjects with at least 1 'not-related' AE	n (%)
R1: Mild	n (%)
R2: Moderate	n (%)
R3: Severe	n (%)
[P4_i_3]: Action taken with Seysara, among Subjects with at least 1 'not-related' AE	
[P4_i_3r1]: Drug withdrawal / study discontinuation	n (%)
Other Actions	n (%)
[P4_i_5]: Subjects with at least 1 SAE*	n (%)
Subjects with at least 1 SAE resulting in death	n (%)

\*for not related AEs.

Note: Percentages were based on the total number of subjects in the study  
Deaths, AEs and SAEs were those that started on or after the date of the first dose of the study treatment and no more than 30 days after the date of the last dose of the study treatment.

**Table 7.4.4.3. AEs (Not-Related) – by Organ Class & Preferred Term (Subject level)**

System Organ Class: Preferred Term	N=300	Intensity	Action Taken*
			Action Taken*
Gastrointestinal disorders	n (%)		
GI Upset	n (%)	A	A
Y	n (%)	B	B
Infections and infestations	n (%)		
X	n (%)	A	A
Y	n (%)	B	B
Injury, poisoning and procedural complication	n (%)	A	
X	n (%)	B	A
Y	n (%)		B
Investigations	n (%)	A	
X	n (%)	B	A
Y	n (%)		B
Nervous system disorders	n (%)	A	
Headache	n (%)	B	A
Y	n (%)		B
Skin and subcutaneous tissue disorders	n (%)	A	
X	n (%)	B	A
Y	n (%)		B
Respiratory, thoracic and mediastinal disorders	n (%)		
X		A	
Y	n (%)	B	A
General disorders and administration site conditions	n (%)		
X	n (%)	B	A
Y	n (%)		B

\*Action taken as a result of the AE.

Note: Percentages were based on the total number of patients in Safety Population, i.e., 300.  
If a same AE occurred more than once for a given patient, the AE was counted only once at Subject-level.  
For any of the safety events, a single patient may have reported more than one event.  
Deaths, AEs and SAEs were those that started on or after the date of the first dose of the study treatment  
and no more than 30 days after the date of the last dose of the study treatment.  
Adverse events were coded using MedDRA version 2021AB.

*This table will be replicated to characterize SAEs, if any observed.*

**Table 7.4.4.4. Overall Summary of ADRs (Subject level)**

N=300	
[P5] Subjects with at least 1 ADR*	n (%)
[P5_i_4]: Intensity of adverse event, among Subjects with at least 1 ADR	n (%)
R1: Mild	n (%)
R2: Moderate	n (%)
R3: Severe	n (%)
[P5_i_3]: Action taken with Seysara, among Subjects with at least 1 ADR	
[P5_i_3r1]: Drug withdrawal / study discontinuation	n (%)
Other Actions	n (%)
[P5a_i_5]: Subjects with at least 1 Serious ADR	n (%)
Subjects with at least 1 Serious ADR, resulting in death	n (%)

\*excludes special safety events.

Note: Percentages were based on the total number of subjects in the study

Deaths, ADRs and Serious ADRs were those that started on or after the date of the first dose of the study treatment and no more than 30 days after the date of the last dose of the study treatment.

**Table 7.4.4.5. ADRs – by Organ Class & Preferred Term (Subject level)**

System Organ Class: Preferred Term	N=300	Intensity	Action Taken*
			Action Taken*
Gastrointestinal disorders	n (%)		
GI Upset	n (%)	A	A
Y	n (%)	B	B
Infections and infestations	n (%)		
X	n (%)	A	A
Y	n (%)	B	B
Injury, poisoning and procedural complication	n (%)		
X	n (%)	A	A
Y	n (%)	B	B
Investigations	n (%)		
X	n (%)	A	A
Y	n (%)	B	B
Nervous system disorders	n (%)		
Headache	n (%)	A	A
Y	n (%)	B	B
Skin and subcutaneous tissue disorders	n (%)		
X	n (%)	A	A
Y	n (%)	B	B
Respiratory, thoracic and mediastinal disorders	n (%)		
X	n (%)	A	A
Y	n (%)	B	B
General disorders and administration site conditions	n (%)		
X	n (%)	A	A
Y	n (%)	B	B

\*Action taken as a result of the AE.

Note: Percentages were based on the total number of patients in Safety Population, i.e., 300.  
If a same ADR occurred more than once for a given patient, the ADR was counted only once at Subject-level. For any of the safety events, a single patient may have reported more than one event.  
Deaths, ADRs and Serious ADRs were those that started on or after the date of the first dose of the study treatment and no more than 30 days after the date of the last dose of the study treatment.  
Adverse events were coded using MedDRA version 2021AB.

*This table will be replicated to characterize Serious ADRs, if any observed.*

**Table 7.4.4.6. Overall Summary of Adverse Events – Any Type (Event Level)**

[P4 or P5] Total number of adverse events (any type)*	N
[P4_i_4 or P5_i_4]: Intensity of adverse events, among documented adverse events (any type)*	
R1: Mild	n (%)
R2: Moderate	n (%)
R3: Severe	n (%)
[P4_i_3 or [P5_i_3]: Action taken with Seysara, for documented adverse events (any type)*	
[P4_i_3r1 or P5_i_3r1]: Drug withdrawal / study discontinuation	n (%)
Other Actions	n (%)
[P4_i_5 or [P5_i_5]: Number of SAEs or Serious ADRs	n (%)
Number of SAEs or Serious ADRs resulting in death	n (%)

\*includes not-related AEs and ADRs (related-AEs); excludes special safety events.

Note: Percentages were based on the total number of adverse events (any type) observed in the study, i.e., N=x.

The same AE or ADR was counted as many times as it occurred, for a given patient. For any of the safety events, a single patient may have reported more than one event.

Deaths, AEs/ADRs, SAEs, and Serious ADRs were those that started on or after the date of the first dose of the study treatment and no more than 30 days after the date of the last dose of the study treatment.

**Table 7.4.4.7. Overall Summary of 'Not-Related' AEs (Event Level)**

[P4] Total number of 'not-related' AE	N
[P4_i_4]: Intensity of adverse event, among documented 'not-related' AEs	n (%)
R1: Mild	n (%)
R2: Moderate	n (%)
R3: Severe	n (%)
[P4_i_3]: Action taken with Seysara, for documented 'not-related' AEs	
[P4_i_3r1]: Drug withdrawal / study discontinuation	n (%)
Other Actions	n (%)
[P4_i_5]: Number of SAEs*	n (%)
Number of SAEs resulting in death	n (%)

\*refers to 'not-related AEs'.

Note: Percentages were based on the total number of 'not-related' AEs observed in the study, i.e., N=x. The same AE was counted as many times as it occurred, for a given patient. For any of the safety events, a single patient may have reported more than one event.

Deaths, AEs and SAEs were those that started on or after the date of the first dose of the study treatment and no more than 30 days after the date of the last dose of the study treatment.

**Table 7.4.4.8. AEs (Not-Related) – by Organ Class & Preferred Term (Event level)**

System Organ Class: Preferred Term	N=x	Intensity	Action Taken*
Gastrointestinal disorders	n (%)		
GI Upset	n (%)	A	A
Y	n (%)	B	B
Infections and infestations	n (%)		
X	n (%)	A	A
Y	n (%)	B	B
Injury, poisoning and procedural complication	n (%)	A	
X	n (%)	B	A
Y	n (%)		B
Investigations	n (%)	A	
X	n (%)	B	A
Y	n (%)		B
Nervous system disorders	n (%)	A	
Headache	n (%)	B	A
Y	n (%)		B
Skin and subcutaneous tissue disorders	n (%)	A	
X	n (%)	B	A
Y	n (%)		B
Respiratory, thoracic and mediastinal disorders	n (%)		
X		A	
Y	n (%)	B	A
General disorders and administration site conditions	n (%)		
X	n (%)	B	A
Y	n (%)		B

\*Action taken as a result of the AE.

Note: Percentages were based on the total number of 'not-related' AEs observed in the study, i.e., N=x. The same AE was counted as many times as it occurred, for a given patient. For any of the safety events, a single patient may have reported more than one event.

Deaths, AEs and SAEs were those that started on or after the date of the first dose of the study treatment and no more than 30 days after the date of the last dose of the study treatment.

Adverse events were coded using MedDRA version 2021AB.

This table will be replicated to characterize SAEs, if any observed.

**Table 7.4.4.9. AEs (Not-Related) – by Patient-ID (Event level)**

<<all events will be reported at Patient-ID level AND ORDERED BY 'System Organ Class and then Preferred Term' >>

Patient-ID # 1	Study/Survey Timepoint	[P4_i] Reported Term for the Adverse Event	AE Preferred Term	Primary System Organ Class
[P4_i_1] Date of Onset	[P4_i_2] Date of Resolution	[P4_i_3] Action taken with Seysara*	[P4_i_4] Intensity of Adverse Event	[P4_i_5] Is this a SAE?
Patient-ID # 2	Study/Survey Timepoint	[P4_i] Reported Term for the Adverse Event	AE Preferred Term	Primary System Organ Class
[P4_i_1] Date of Onset	[P4_i_2] Date of Resolution	[P4_i_3] Action taken with Seysara*	[P4_i_4] Intensity of Adverse Event	[P4_i_5] Is this a SAE?

\*Action taken as a result of the AE.

Deaths, AEs and SAEs were those that started on or after the date of the first dose of the study treatment and no more than 30 days after the date of the last dose of the study treatment.

Adverse events were coded using MedDRA version 2021AB.

**Table 7.4.4.10. Overall Summary of ADRs (Event level)**

[P5] Total number of ADRs*	N
[P5_i_4]: Intensity of adverse events, among documented ADRs	
R1: Mild	n (%)
R2: Moderate	n (%)
R3: Severe	n (%)
[P5_i_3]: Action taken with Seysara, for documented ADRs	
[P5_i_3r1]: Drug withdrawal / study discontinuation	n (%)
Other Actions	n (%)
[P5a_i_5]: Number of Serious ADR	n (%)
Number of Serious ADR, resulting in death	n (%)

\*excludes special safety events.

Note: Percentages were based on the total number of ADRs observed in the study, i.e., N=x.

The same ADR was counted as many times as it occurred, for a given patient. For any of the safety events, a single patient may have reported more than one event.

Deaths, ADRs and Serious ADRs were those that started on or after the date of the first dose of the study treatment and no more than 30 days after the date of the last dose of the study treatment.

**Table 7.4.4.11. ADRs – by Organ Class & Preferred Term (Event level)**

System Organ Class: Preferred Term	N=x	Intensity	Action Taken*
Gastrointestinal disorders	n (%)		
GI Upset	n (%)	A	A
Y	n (%)	B	B
Infections and infestations	n (%)		
X	n (%)	A	A
Y	n (%)	B	B
Injury, poisoning and procedural complication	n (%)		
X	n (%)	A	A
Y	n (%)	B	B
Investigations	n (%)		
X	n (%)	A	A
Y	n (%)	B	B
Nervous system disorders	n (%)		
Headache	n (%)	A	A
Y	n (%)	B	B
Skin and subcutaneous tissue disorders	n (%)		
X	n (%)	A	A
Y	n (%)	B	B
Respiratory, thoracic and mediastinal disorders	n (%)		
X	n (%)	A	A
Y	n (%)	B	B
General disorders and administration site conditions	n (%)		
X	n (%)	A	A
Y	n (%)	B	B

\*Action taken as a result of the AE.

Note: Percentages were based on the total number of ADRs observed in the study, i.e., N=x.

The same ADR was counted as many times as it occurred, for a given patient. For any of the safety events, a single patient may have reported more than one event.

Deaths, ADRs and Serious ADRs were those that started on or after the date of the first dose of the study treatment and no more than 30 days after the date of the last dose of the study treatment.

Adverse events were coded using MedDRA version 2021AB.

*This table will be replicated to characterize Serious ADRs, if any observed.*

**Table 7.4.4.12. ADRs – by Patient-ID (Event level)**

<<all events will be reported at Patient-ID level AND ORDERED BY 'System Organ Class and then Preferred Term' >>

Patient-ID # 1	Study/Survey Timepoint	[P5_i] Reported Term for the Adverse Event	Preferred Term	Primary System Organ Class

[P5_i_1] Date of Onset	[P5_i_2] Date of Resolution	[P5_i_3] Action taken with Seysara*	[P5_i_4] Intensity of Adverse Event	[P5_i_5] Is this a SAE?

Patient-ID # 2	Study/Survey Timepoint	[P5_i] Reported Term for the Adverse Event	Preferred Term	Primary System Organ Class

[P5_i_1] Date of Onset	[P5_i_2] Date of Resolution	[P5_i_3] Action taken with Seysara*	[P5_i_4] Intensity of Adverse Event	[P5_i_5] Is this a SAE?

\*Action taken as a result of the ADR.

Deaths, ADRs and Serious ADRs were those that started on or after the date of the first dose of the study treatment and no more than 30 days after the date of the last dose of the study treatment.

Adverse events were coded using MedDRA version 2021AB.

**Table 7.4.4.13. Summary of Other Safety Events (Subject Level)**

Safety events	N=300
[P6]: Lack of effectiveness	n (%)
[P7]: Drug overdose	n (%)
[P8]: Off-label use	n (%)
[P9]: Misuse	n (%)
[P10]: Abuse	n (%)
[P11]: Medication errors	n (%)
[P12]: Occupational exposure	n (%)

Note: Table portrays number of unique subjects with at least one event in respective categories. Denominator for percentages is the total number of patients (N=300).

**Table 7.4.4.14. Summary of Other Safety Events (Event Level)**

Safety events	N=X
[P6]: Lack of effectiveness	n (%)
[P7]: Drug overdose	n (%)
[P8]: Off-label use	n (%)
[P9]: Misuse	n (%)
[P10]: Abuse	n (%)
[P11]: Medication errors	n (%)
[P12]: Occupational exposure	n (%)

Note: Table portrays number of unique safety events, allowing for multiple events per patients. Denominator for percentages is the total number of events during the treatment period (N=x).

**Table 7.4.5. Adult Patient & Caregiver Demographic Characteristics**

Adult Demographic Data	Caregiver (N=x)	Adult Patient (N=x)	Total (N=300)
S2: Age	mean (SD) Median Min, Max	mean (SD) Median Min, Max	mean (SD) Median Min, Max
S8: Gender			
Male	n (%)	n (%)	n (%)
Female	n (%)	n (%)	n (%)
S9: Marital Status			
Not Married	n (%)	n (%)	n (%)
Not Marries, living with Partner	n (%)	n (%)	n (%)
Married or Civil Union	n (%)	n (%)	n (%)
Divorced or Separated	n (%)	n (%)	n (%)
Widow/Widower	n (%)	n (%)	n (%)
Prefer not to answer	n (%)	n (%)	n (%)
S10: Highest level of Education			
Less than high school diploma/degree	n (%)	n (%)	n (%)
High school degree or equivalent (e.g., GED)	n (%)	n (%)	n (%)
Some college but not degree	n (%)	n (%)	n (%)
Associated degree	n (%)	n (%)	n (%)
Bachelor's degree	n (%)	n (%)	n (%)
Graduate degree	n (%)	n (%)	n (%)
Prefer not to answer	n (%)	n (%)	n (%)
S11: Employment status			
Employed/Working full-time (paid)	n (%)	n (%)	n (%)
Employed/Working part-time (paid)	n (%)	n (%)	n (%)
Homemaker	n (%)	n (%)	n (%)
Student	n (%)	n (%)	n (%)
Retired	n (%)	n (%)	n (%)
Unemployed	n (%)	n (%)	n (%)
S12: Annual household income			
\$20,000 or less	n (%)	n (%)	n (%)
\$20,001-\$50,000	n (%)	n (%)	n (%)
\$50,001-100,000	n (%)	n (%)	n (%)
\$100,001 or more	n (%)	n (%)	n (%)
Prefer not to answer	n (%)	n (%)	n (%)
S13: Regions/States			
Northeast	n (%)	n (%)	n (%)
Midwest	n (%)	n (%)	n (%)

West	n (%)	n (%)	n (%)
South	n (%)	n (%)	n (%)
S14: Number of children (aged 0 to 17)			
No children	n (%)	n (%)	n (%)
1	n (%)	n (%)	n (%)
2	n (%)	n (%)	n (%)
3	n (%)	n (%)	n (%)
4	n (%)	n (%)	n (%)
More than 4	n (%)	n (%)	n (%)
S16: Primary Health Insurance			
Private health insurance	n (%)	n (%)	n (%)
Medicaid	n (%)	n (%)	n (%)
Medicare	n (%)	n (%)	n (%)
Uninsured	n (%)	n (%)	n (%)
S17: Race/Ethnicity*			
S17r1: White	n (%)	n (%)	n (%)
S17r2: Black or African American	n (%)	n (%)	n (%)
S17r3: American Indian or Alaska Native	n (%)	n (%)	n (%)
S17r4: Asian	n (%)	n (%)	n (%)
S17r5: Native Hawaiian or other Pacific Islander	n (%)	n (%)	n (%)
S17r6: Other	n (%)	n (%)	n (%)
S17r7: Prefer not to answer	n (%)	n (%)	n (%)
S18: Hispanic, Latino, or of Spanish Origin			
Yes	n (%)	n (%)	n (%)
No	n (%)	n (%)	n (%)

\*Not mutually exclusive. Note: Data from Patient DCF

Note: Data from Clinician DCF. Percentages are based on the total sample within respective groups.

**Table 7.4.6. Pediatric Patient Demographic Characteristics**

Pediatric Demographic Data (N=x)		
S3: Age	mean, SD, Median Min, Max	
S21: Gender		
Male	n (%)	
Female	n (%)	
S22: Race/Ethnicity*		
S22r1: White	n (%)	
S22r2: Black or African American	n (%)	
S22r3: American Indian or Alaska Native	n (%)	
S22r4: Asian	n (%)	
S22r5: Native Hawaiian or other Pacific Islander	n (%)	
S22r6: Other	n (%)	
S22r7: Prefer not to answer	n (%)	
S23: Hispanic, Latino, or of Spanish Origin		
Yes	n (%)	
No	n (%)	
S24: Child's Academic Accomplishments		
Current/Last grade completed:		
Pre-K - 5 th grade	n (%)	
6 th grade – 8 th grade	n (%)	
9 th grade – 12 th grade	n (%)	
High School Diploma/Degree	n (%)	
Vocational School	n (%)	
Not currently enrolled in school	n (%)	
S24oe: Other	n (%)	

\*Not mutually exclusive

Note: Data from Clinician DCF. Percentages are based on the total pediatric sample of N=x.

**Table 7.4.7. Patient Disposition Throughout the Study**

This will be summarized, accounting for N=300 for each study visit.

**Table 7.4.8. Significant Protocol Deviations**

This will be summarized, if any observed.

## 7.5 Sensitivity Analyses

Analyses of ASIS Items 9 & 10 that utilized LOCF imputation:

- Tables 7.1.12, 7.1.13: Depict stats without imputation
- 7.1.14 and 7.1.15: Depict stats without imputation

Analyses of clinician IGA related endpoints that utilized LOCF imputation:

- Tables 7.2.4.1, 7.2.4.2, 7.2.4.3: Depict stats without imputation
- Tables 7.2.4.4, 7.2.4.6, 7.2.4.7: Depict stats with imputation

Analysis of clinician IGA related endpoints (with imputation), stratified by type of subject visit are depicted below.

[figure not shown]

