### **3.1 Subject Inclusion Criteria**

**Patient Inclusion Criteria:** In order to be eligible to participate in this study, an individual must meet all of the following criteria:

- Male or female, aged 9 years and above at the time of study recruitment.
- Has facial non-nodular AV with IGA score of moderate (3) or severe (4).
- Considered as a potential candidate for sarecycline treatment to manage their AV, per clinician's judgment.
- Able to read and write English.
- Provide consent (in case of adult patients) or assent (in case of pediatric patients) to participate in the study.
- Willing to comply with all study procedures and be available for the duration of the study.

**Caregiver Inclusion Criteria:** In order to be eligible to participate in this study, an individual must meet all of the following criteria:

- Male or female, aged 18 years and above.
- Able to read and write English.
- Primary caregiver of the study-eligible patient.
- Provide consent to participate in the study.
- Willing to comply with all study procedures and be available for the duration of the study.

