#### **5.3.1 *Investigator Assessments***

An IGA scale of 0 (Clear) to 4 (Severe) was used by the Site Investigators to assess the severity of a subject's facial acne at the time of study encounters. The IGA is representative of the investigator's overall general assessment of the subject's Acne and takes into account the quality, as well as the quantity, of lesions. These assessments were done at baseline encounter to document AV severity before initiation of sarecycline treatment; the assessments were repeated by the Site Investigators at study subject follow-up encounters at Weeks 4, 8 & 12, post-index

date. The comparison of follow-up assessments to the baseline assessment will help determine treatment effectiveness. All Investigator assessments were conducted via in-person visits/encounters at baseline and week-12. The same evaluator performed all evaluations for a subject during the study.

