## 6.5 Secondary Endpoint Analysis

The secondary endpoint of the study is the proportion of Subjects with Facial IGA success at Week 12, defined as  $\geq 2$ -point decrease in IGA score from baseline and a score of 0 (clear) or 1 (almost clear) at Week 12. The analyses of IGA success will be conducted for the overall cohort (using the FAS dataset). LOCF data imputation method will be used to impute responses at Week 12 for the Subjects with missing data at Week 12. Relationship between this endpoint (with LOCF imputation) and subject characteristics will be explored using descriptive analyses, by leveraging subgroup analysis outlined in Section 6.3.2.

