## **6.9 Missing Data Handling**

The missing data pertinent to the validated instrument ASIS will be handled per instrument owner instructions / scoring manual. For effectiveness measures obtained from Site Investigators and Subjects, namely, IGA, PtGA (from ASIS item # 9) and Patient appearance rating scale (from ASIS item # 10), LOCF data imputation method will be used to impute

responses for Week 12 for the Subjects with missing data at Week 12. LOCF will also be used to impute responses for Weeks 4 & 8 for the Subjects with missing data at those encounters for these select measures, as appropriate. For all other study variables and endpoints, no missing data imputation is planned.

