## 6.11 Sensitivity Analyses

Sensitivity analyses will explore the impact of critical missing data or variation in study procedures on the robustness of the results. Specifically:

- Primary and secondary endpoints at Week-12 will be analyzed as is (with missing data, if any) and by using missing data imputation methods (using LOCF; in case of missing data observed), and results portrayed separately for comparison.
- If some Subject visits are conducted via remote visits instead of in-person visits, the nature of visit (remote vs. in-person) may be used to stratify the analysis of secondary endpoint

(involving IGA) and results portrayed separately for comparison with the overall (aggregate) results.

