**Table 7.5.1 Sub-group Analysis of IGA (with LOCF imputation)**

IGA Success / % Clear/Almost Clear	Weeks			
	Baseline	Week 4	Week 8	Week 12
Subject visit type				
In-person visit	n (%)	n (%)	n (%)	n (%)
Remote/	n (%)	n (%)	n (%)	n (%)
Tele-health visit				

**Note:** Facial IGA success at Week 12 (and at Wks 4 & 8), defined as a 2-point decrease in IGA score from baseline and a score of 0 (clear) or 1 (almost clear) at Week 12.

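### Table 7.5.1 compares in-person with remote IGA on LOCF scores only, with no rule for the visit type of a carried-forward score, so missing visits can pass for an effect of assessment mode

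*SAP*

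**What the plan says.** SAP 6.11 lists two sensitivity analyses. One repeats the Week 12 endpoints with and without LOCF. The other applies if some visits were remote, in which case "the nature of visit (remote vs. in-person) may be used to stratify the analysis of secondary endpoint".

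SAP 7.5 implements the second: "Analysis of clinician IGA related endpoints (with imputation), stratified by type of subject visit are depicted below". The table it points to, Table 7.5.1, is titled as an LOCF analysis and has in-person and remote rows at Baseline and Weeks 4, 8 and 12. The other overall IGA results listed in 7.5 appear both without imputation (Tables 7.2.4.1 to 7.2.4.3) and with it (Tables 7.2.4.4, 7.2.4.6 and 7.2.4.7). Table 7.5.1 has no unimputed partner, although Protocol 12.8 says LOCF results will be shown alongside results without LOCF.

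On imputation, SAP 6.5 says "LOCF data imputation method will be used to impute responses at Week 12 for the Subjects with missing data at Week 12", and SAP 6.9 adds "LOCF will also be used to impute responses for Weeks 4 & 8 for the Subjects with missing data at those encounters". SAP 6.9 plans no imputation for variables other than IGA and ASIS items 9 and 10.

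On visit type, item M1A.2 in Table 7.2.4.1 (the unimputed IGA table) records how each evaluation was done, with a telehealth option at every visit. The LOCF counterpart, Table 7.2.4.4, has no visit-type rows. SAP 5.3.1 reports that "All Investigator assessments were conducted via in-person visits/encounters at baseline and week-12". Appendix A footnote 5 permits remote IGA assessment generally.

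**The concern.** Visit type is a property of a rating that took place. A carried-forward score was not rated at the encounter where it is tabulated, so it has no visit type there. Table 7.5.1 needs one to place the patient in a row, and the SAP does not say how to assign it. The programmer would have to invent the rule.

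The choice matters because carried-forward scores are not neutral. At Week 4 the only earlier score is baseline, which eligibility fixes at 3 or 4 (SAP 3.1). Whichever row receives those patients is pulled down. A table meant to show whether mode of assessment affects IGA could then show a difference produced by missed visits, with its direction set by an undocumented programming decision.

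**Working it through.** The plan gives no figure to reproduce: it has no IGA rates, no missing-data rate and no share of remote visits. The check is one of logic, followed by an illustration under stated assumptions.

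**Step 1: what LOCF does at Week 4.** Baseline 3 carried forward is 3; baseline 4 carried forward is 4. The change is 0 and the score is not 0 or 1. That is a non-success whether the two-point criterion is read as exactly 2 or at least 2, and it is not clear or almost clear. The imputed success rate is 0% by construction.

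**Step 2: a false gap at Week 4.** Let p be the true rate, equal in both modes; m the share of patients with a missing score; r the remote share of observed visits. Take p = 20%, m = 10%, r = 30%. Per 100 patients:

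- observed in person: 100 × 0.90 × 0.70 = 63, of whom 0.20 × 63 = 12.6 succeed
- observed remote: 100 × 0.90 × 0.30 = 27, of whom 0.20 × 27 = 5.4 succeed
- missing, imputed as non-success: 10

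Three possible rules give three tables:

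| Rule for imputed scores | In person | Remote |
|---|---|---|
| Keep source visit's type (baseline, in person) | 12.6 / 73 = 17.3% | 5.4 / 27 = 20.0% |
| Placed in remote row | 12.6 / 63 = 20.0% | 5.4 / 37 = 14.6% |
| No visit type, so left out | 12.6 / 63 = 20.0% | 5.4 / 27 = 20.0% |

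The true difference is zero in every line.

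**Step 3: range under the source-visit rule.** The false gap is p·m / [(1−r)(1−m) + m]. Over p = 10–40%, m = 5–20% and r = 10–50%:

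- smallest: 0.10 × 0.05 / (0.90 × 0.95 + 0.05) = 0.005 / 0.905, about 0.6 points
- largest: 0.40 × 0.20 / (0.50 × 0.80 + 0.20) = 0.08 / 0.60, about 13.3 points

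**Step 4: Week 12.** If SAP 5.3.1 is correct, no observed Week 12 rating was remote, and none was remote at baseline. A remote entry at Week 12 could come only from a remote Week 4 or Week 8 rating carried forward. Section 7.2 restricts IGA evaluations, where relevant, to FAS patients with Week 12 clinician data. If that also governs Table 7.5.1, nothing needs imputing at Week 12 and the remote row is empty.

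**The case against.** The strongest counter-argument is that the SAP's own text may prevent the bias. Section 6.9 does not extend imputation to visit type, so M1A.2 stays missing for a missed visit. A programmer stratifying on it would drop the imputed patients, leaving observed data and no false gap (the third rule above). That is a fair reading, but it would make the table an observed-data analysis under an LOCF title. The plan should say which is meant.

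A reader might infer that the Week 12 remote row must consist of carried-forward values. The documents do not support this. The row may simply be empty, and the premise is unsettled: SAP 5.3.1 sits beside the conditional wording of 6.11, the telehealth cells in Table 7.2.4.1 and the permission in Appendix A. If SAP 5.3.1 is inaccurate, observed remote ratings could exist at Week 12.

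A reader might also infer that the table can say nothing about mode, or that the in-person row is necessarily understated. Neither follows. Observed remote ratings at Weeks 4 and 8 would still appear, and the direction depends on the missing rule.

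The amount of missing data may also be small. SAP 6.2 limits the FAS in essence to patients who completed the Week 12 survey, so Week 4 gaps are intermittent. The analysis is optional, and overall IGA is already shown with and without LOCF, though not by visit type.

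**Conclusion.** The point holds as a minor defect of specification. Table 7.5.1 uses LOCF scores only, has no observed-data counterpart, and lacks a rule for the visit type of an imputed score. If imputed patients are placed in a row, Week 4 mixes missingness with mode of assessment.

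The size is illustrative: 2.7 points in the middle case and about 0.6 to 13.3 points across the range, both under the source-visit rule; the middle case reverses to 5.4 points the other way (20.0 − 14.6) if imputed scores go to the remote row. These figures assume equal true rates in the two modes and unsourced values for p, m and r. If imputed patients are left out of both rows, the gap is zero.

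The Week 12 conclusion depends on SAP 5.3.1 being accurate. On that footing the table contains no observed remote rating at Week 12, so the secondary endpoint cannot be compared by mode. The main IGA result is unaffected.

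**What to change.** - Build Table 7.5.1 from observed IGA (the data behind Table 7.2.4.1), classing each rating by its own M1A.2 entry at that encounter.
- At Weeks 4 and 8, show N for each row and the missing counts.
- Show Week 12 only if observed remote Week 12 ratings exist.
- Reconcile SAP 5.3.1 with SAP 6.11, Table 7.2.4.1 and Appendix A footnote 5 on whether baseline and Week 12 ratings could be remote.
- If an LOCF version is kept as well, state the visit-type rule for imputed scores in the table note.

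The cost is a change of input dataset for one table, using data already collected, and fewer patients per row. Visit type is not assigned by design, so even the corrected table describes ratings by mode and does not isolate the effect of mode.
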